4.5 Subject Disposition

The number of subjects and the reasons for discontinuation (adverse events, protocol deviation, lost to follow-up, death, etc.) of study treatment and discontinuation from study will be listed and summarized by group (by cohort and overall) for the Enrolled Population.

A data listing will be provided to define each cohort and identify subjects by cohort.

Additionally, a listing of screen failures will be provided identifying reasons why they were not enrolled.

4.6 Demographic and Baseline Characteristics

Descriptive summary statistics (n, mean, standard deviation, median, minimum, and maximum) and/or frequency distributions, as appropriate, will be provided by group (y cohort and overall) for the Safety Population. Demographic characteristics summarized will include, age, sex, race, and ethnicity. Baseline information summarized will include Status Epilepticus Severity Score (STESS), epileptic history, and status epilepticus (SE) history. Demographic characteristics and baseline STESS and epileptic history will also be listed.

Other than these characteristics, baseline values for safety and efficacy parameters will be summarized in respective tables.

4.7 Protocol Violations

Protocol violations will be identified prior to database lock to measure adherence to key aspects of the protocol. List of protocol deviations will be prepared before database lock. Specific data fields that will be examined to identify protocol violations include inclusion/exclusion criteria and prohibited prior and concomitant treatments as well as deviations identified by the investigator. All protocol violations will be listed for the Safety Population.

4.8 Efficacy Analyses

All efficacy analyses will be conducted for the Safety Population.

Considering that data from only open-label phase is available for analysis, efficacy assessments are only summarized and listed. There will be no statistical inferential test of any efficacy endpoint.

4.8.1 Status Epilepticus (SE) and Seizure

Status epilepticus and seizure questions will be listed and summarized by group (by cohort and overall) and time point. Additionally, SE cessation time will be listed and summarized (by cohort and overall).

4.8.2 Seizure Burden

Seizure burden will be listed and summarized by group (by cohort and overall) and time point.

4.8.3 Clinical Global Impression of Severity and Improvement (CGI-S and CGI-I)

The CGI-S and CGI-I scores will be listed and summarized by group (by cohort and overall) and time point.

4.8.4 Glasgow Coma Scale (GCS) of Pediatric Glasgow Coma Scale (PGCS)

The GCS or PGCS scores will be listed and summarized by group (by cohort and overall) and time point. Both observed values and change from baseline will be listed and summarized.

4.8.5 Richmond Agitation and Sedation Scale (RASS)

The RASS scores will be listed and summarized by group (by cohort and overall) and time point.

4.8.6 Mini-Mental State Examination (MMSE)

The MMSE total scores will be listed by cohort, subject, and time point.

4.8.7 Detailed Monitoring of EEG Data

Data collected from detailed monitoring of EEG activities will be listed and summarized.

4.9 Safety Analyses

The comprehensive safety analysis is based on all subjects in the Safety Population, unless indicated in the individual safety endpoint analysis. Safety data will be listed and summarized by group (by cohort and overall). The following sections detail the analyses performed on the safety data.

4.9.1 Adverse Events

Adverse events are coded using the MedDRA dictionary, Version 20.1 or higher, and are categorized by system organ class (SOC) and preferred term (PT). Only treatment emergent adverse events are included in the summary tabulations. All adverse events are included in the data listings.

To allow differentiation as to which study period an Adverse Event occurred, two categories are defined based upon onset date. Adverse Events that had onset dates prior to the first dose of study medication are considered "prior". Adverse events with onset dates on or after the first dose of study medication and up to end of follow-up period are considered "on-therapy" or equivalently "treatment emergent". Adverse events with an onset date prior to the first dose of study medication but worsens after treatment starts are considered a treatment emergent AE.

Overall summary of Treatment-emergent adverse events (TEAE) will be provided. The TEAEs will be summarized by MedDRA System Organ Class (SOC) and preferred term (PT), and by group (by cohort and overall). Treatment-emergent adverse events will further be summarized by severity and relationship to treatment medication. Treatment-emergent Serious Adverse Events (SAE) and AEs leading to discontinuation of study drug will also be summarized by SOC, PT, and group (by cohort and overall).

Adverse events and serious adverse events will be listed.

Deaths will be listed and summarized by group (by cohort and overall).

4.9.2 Medical History

Medical history information recorded in eCRF will be listed for the Enrolled Population by cohort and subject.

4.9.3 Prior and Concomitant Treatments and Procedures

Prior treatment includes all non-study treatment received within 30 days prior to the first dose of study medication. Concomitant treatment refers to all treatment taken between the date of the first dose of study medication and the last follow-up visit/contact and are recorded in eCRF pages.

Prior and concomitant medications (Non-AEDs) will be listed and summarized by group (by cohort and overall). Antiepileptic drugs (AEDs) are also collected as part of prior and concomitant treatments. A separate listing and summary table will be presented for AEDs.

Additionally, Prior and concomitant Procedures and Anesthetics will be listed and summarized by group (by cohort and overall).

Medications are coded using the WHO Drug dictionary.

4.9.4 Physical Examination

Physical examination results will be reported for the Safety Population.

Physical examination abnormal findings at baseline will be listed for each subject. Any changes in physical examination findings in subsequent time points from previous time point will also be listed.

4.9.5 Vital Signs

Vital signs are listed and summarized by time point and group (by cohort and overall) for the Safety Population. Systolic blood pressure, diastolic blood pressure, pulse, respiration rate, temperature, oxygen saturation, height, weight, and body mass index (BMI) will be summarized and listed. Both observed values and change from baseline will be summarized.

4.9.6 Laboratory Evaluations

Laboratory findings will be listed and summarized for the Safety Population.

Chemistry, hematology, and urinalysis parameter results will be summarized using descriptive statistics by time point and group (by cohort and overall). Both actual values and change from baseline will be summarized. Similar table will be provided for AED laboratory results.

Summary showing number and percent of subjects with abnormal laboratory test results will be provided by time point and group (by cohort and overall) for hematology, chemistry, and urinalysis parameters.

Lab results, including AEDs, will be listed by cohort, subject, and time point.

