**Rationale:**

Status epilepticus (SE) is defined as a prolonged self-sustaining seizure or recurrent seizures without recovery of consciousness between seizures. The International League of Against Epilepsy further defined SE as a condition resulting either from the failure of mechanisms responsible for seizure termination or from the initiation of mechanisms, which lead to abnormally, prolonged seizures (5 minutes for tonic-clonic SE and 10 minutes for focal SE with impaired consciousness) and which can have long-term consequences (after 30 minutes for tonic-clonic SE and >60 minutes for focal SE with impaired consciousness), including neuronal death and/or injury, and alteration of neuronal networks, depending on the type and duration of seizures. SE is a neurological emergency that requires aggressive treatment to stop the seizures and prevent permanent neurological damage. Mortality due to SE can range from 3% to 40% depending on etiology, age, SE type, and SE duration. SE can be recognized clinically or using electroencephalograms (EEGs) by the presence of continuous ictal discharges. Studies have shown that SE can cause neuronal death via excitotoxic mechanisms as a result of excessive neuronal firing. Furthermore, convulsive SE is associated with many complications, including cardiac arrhythmias, rhabdomyolysis, pulmonary edema, electrolyte and glucose imbalance, and temperature disturbances. Approximately one third of subjects with refractory status epilepticus (RSE) and super refractory status epilepticus (SRSE) will die of their condition; one-third recover but with chronic neurologic or other deficits, and one third have been generally described as returning to baseline. The prognosis worsens the longer subjects are kept in a medically-induced coma. The primary goal of SE treatment is to gain control of the seizures rapidly and avoid complications, and treatment typically occurs in stages. In general, the treatment of SE is very aggressive and particularly urgent for convulsive status epilepticus (CSE).

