#### **4.2 Exclusion Criteria**

Subjects are excluded from the study if any of the following exclusion criteria are met.

1. Life expectancy of less than 24 hours
2. Anoxic brain injury as the primary cause of SE
3. Recent (< 24 hour) traumatic brain injury as the primary cause of SE

4. Administered anesthesia (3rd line treatment; e.g., midazolam, propofol, thiopental, pentobarbital, or ketamine) at adequate doses and duration for the treatment of the current episode of SE that required the subject to be hospitalized and 5 half-lives of the agent used has not elapsed
5. Subjects who are intubated for the administration of an IV anesthetic drug (a 3rd line treatment; e.g., midazolam, propofol, thiopental, pentobarbital, or ketamine) to treat SE; subjects who are intubated for airway protection are not excluded
6. Subjects known or suspected to be pregnant upon screening
7. To the best knowledge of the investigator, has allergy to progesterone or allopregnanolone medications/supplements or has previously received ganaxolone or exogenous allopregnanolone
8. If renal impairment is suspected (eGFR  $\leq$  45 mL/min) or subject is currently on dialysis; if decision is made to start dialysis during study participation, subject is not excluded.
9. To the best knowledge of the investigator, subject has hepatic insufficiency at screening, for example alanine transferase or aspartate transferase level more than 5 times the upper limit of normal (ULN), or total bilirubin more than 2 times ULN at the screening visit
10. Subjects with a durable medical care agreement that would not allow hospital to administer their standard of care for treatment of SE
11. Subjects on an investigational drug that is not recommended by treatment guidelines are required to have a reasonable expectation that the investigational study drug has been cleared from their system, that is, that five half-lives have elapsed
12. Subjects who have a history or evidence of a medical condition that, in the investigator's judgment, would expose subject to an undue risk of a significant adverse event or interfere with assessments of safety or efficacy during the course of the study

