#### **8.1.5 Clinical Laboratory and Other Safety Evaluations**

A change in the value of a clinical laboratory, vital sign, or ECG assessment can represent an AE if the change is clinically significant or if, during treatment with the study drug, a shift of a parameter is observed from a normal value to an abnormal value, or there is a further worsening of an already abnormal value. When evaluating such changes, the extent of deviation from the reference range, the duration until return to the reference range (either while continuing treatment or after the end of treatment with the study drug), and the range of variation of the respective parameter within its reference range must be taken into consideration.

For subjects who complete the study and don't progress to an IV anesthetic drug (a 3rd line treatment) for seizure suppression, if, at the end of the treatment phase, there are abnormal clinical laboratory, vital sign, or ECG values that were not present in the pretreatment findings observed closest to the start of study drug initiation, further investigations should be performed until the values return to within the reference range or until a plausible explanation (e.g., concomitant disease) is found for the abnormal values.

The investigator should decide, based on the above criteria and the clinical condition of a subject, whether a change in a clinical laboratory, vital sign, or ECG parameter is clinically significant and therefore represents an AE.

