4.4 General Analysis and Reporting Convention

Since data from only open-label phase are analyzed, there will be only one treatment group. For efficacy and safety summaries, where applicable, subjects will be categorized into three cohorts (Cohort 1: High, Cohort 2: Medium, and Cohort 3: Low) based upon target dose of study medication. An overall group will also be reported representing all subjects.

General Convention:

The following are general conventions for the analysis of study data. If alternative methods are present in the specific evaluation sections of this SAP, those conventions will take precedence over these general conventions.

- Continuous study measurements will be summarized by treatment group (Open-Label Group or Cohorts and Open-Label Group) and time point (as applicable) using descriptive statistics (n, mean, standard deviation, median, minimum, and maximum). Means and medians will be presented with one more decimal place than the precision of the data. Standard deviations will be presented with two more decimal places than the precision of the data. Minimums and maximums will be presented with the same precision as the original data.

- Categorical study assessments will be summarized by treatment group (Open-Label Group or Cohorts and Open-Label Group) and time point (as applicable) using frequency counts and percentages. Unless stated otherwise, percentages are based on the number of subjects in the treatment group of the analysis set. Percentages will be presented with one decimal place (xx.x), with the exception of 100%, which will be displayed without any decimal places.
- Descriptive summaries based on the modified ITT (mITT) analysis set and per-protocol (PP) analysis set will be displayed by randomized treatment.
- Descriptive summaries based on the safety analysis set will be displayed by actual treatment received.
- All listings will be listed by cohort, subject, and time point (if applicable).
- Scheduled assessments will be included in summaries. Unscheduled assessments will only be included in the display sections that report abnormal laboratory, vitals, or ECG values. Data from all assessments (scheduled and unscheduled), will be included in listings.
- All statistical tests will be performed at a significance level of 0.05 (two-tailed). Where applicable, two-sided 95% confidence intervals will be reported. For tables.

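### The SAP's abnormal-laboratory table ignores baseline, so it cannot count new or worsened abnormalities and resolving cases can offset new ones

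*SAP*

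**What the plan says.** SAP 4.9.6 plans three laboratory outputs for the Safety Population.

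- Descriptive statistics by time point and group: "Both actual values and change from baseline will be summarized". SAP 4.4 defines these statistics as n, mean, SD, median, minimum and maximum.
- A categorical table: "Summary showing number and percent of subjects with abnormal laboratory test results will be provided by time point and group".
- Listings: "Lab results, including AEDs, will be listed by cohort, subject, and time point".

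Two conventions in SAP 4.4 govern the categorical table. Unless stated otherwise, "percentages are based on the number of subjects in the treatment group of the analysis set". On extra samples: "Unscheduled assessments will only be included in the display sections that report abnormal laboratory, vitals, or ECG values". SAP 4.4 also defines baseline as the last assessment before dosing, but 4.9.6 does not apply it to the abnormal-results table. The SAP contains no shift table, no definition of a treatment-emergent laboratory abnormality and no criteria for potentially clinically important values.

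The protocol describes the change of interest in within-subject terms. Under Protocol 8.1.5 a laboratory change can represent an adverse event if it is clinically significant, or if during treatment "a shift of a parameter is observed from a normal value to an abnormal value", or if an already abnormal value worsens further. Protocol 9.8 also says that potentially clinically important findings will be summarized or listed.

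**The concern.** Only the open-label group was run (SAP 1, 3.6 and 3.7). There is no control arm, so each subject's own pre-dose value is the only reference for laboratory safety. The one table that counts subjects does not use it.

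Abnormal values at entry are plausible on the documents. The protocol's synopsis rationale lists complications of convulsive status epilepticus "including cardiac arrhythmias, rhabdomyolysis, pulmonary edema, electrolyte and glucose imbalance, and temperature disturbances". The example of hepatic insufficiency in exclusion 9 (Protocol 4.2) begins above 5 times the upper limit of normal (ULN) for the transaminases and above 2 times for bilirubin. Exclusion 8 sets the renal limit at an eGFR of about 45 mL/min. Lesser abnormalities can therefore enter, and those caused by the seizures may resolve as the seizures stop.

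At stake is how readable the hepatic and renal safety data are. Protocol 2.1 records that the FDA allowed up to 50 g/day of Captisol after weighing benefit against the risk of high exposure, and would want clinical experience between 35 and 50 g/day before considering more.

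**Working it through.** The plan states no figure on this point, so there is none to reproduce. The check is a counting identity.

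**Inputs.** N = 30, the upper size of the open-label group in the protocol synopsis. Let b be the number abnormal at baseline, n the number newly abnormal and r the number resolved. The documents give none of these three, so they are assumed and varied. No missing values are assumed.

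**Formulas.**
- Planned table at a later time point: (b + n − r) / N
- New abnormality among those at risk: n / (N − b)

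| b | n | r | Planned table, before | Planned table, after | New among baseline-normal |
|---|---|---|---|---|---|
| 12 | 0 | 0 | 12/30 = 40.0% | 12/30 = 40.0% | 0/18 = 0.0% |
| 12 | 3 | 3 | 40.0% | 12/30 = 40.0% | 3/18 = 16.7% |
| 12 | 6 | 6 | 40.0% | 12/30 = 40.0% | 6/18 = 33.3% |
| 12 | 3 | 6 | 40.0% | 9/30 = 30.0% | 3/18 = 16.7% |
| 6 | 6 | 6 | 6/30 = 20.0% | 6/30 = 20.0% | 6/24 = 25.0% |
| 18 | 6 | 6 | 18/30 = 60.0% | 18/30 = 60.0% | 6/12 = 50.0% |
| 18 | 6 | 0 | 60.0% | 24/30 = 80.0% | 6/12 = 50.0% |

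The first three rows look identical in the planned table. The fourth looks like improvement although three subjects became abnormal. In the last row nothing resolves and the rise is visible, so offsetting depends on resolution.

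**Upper bound.** With an unchanged percentage, the most new cases that can be offset is min(b, 30 − b): 3 for b = 3, 6 for b = 6, 9 for b = 9, 12 for b = 12, 15 for b = 15 and 12 for b = 18.

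**Two gaps that need no resolving cases.** A subject whose ALT goes from 2 to 8 times ULN (an assumed example) is abnormal at both times and adds nothing to the count. No direction is specified either, so a value that goes from low to high can count as abnormal at both times.

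**Denominator.** If x subjects are abnormal and m of the 30 have no sample at a time point, the SAP 4.4 default gives x/30 rather than x/(30 − m). Missing samples therefore lower the displayed percentage.

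**Other outputs.** The maximum change from baseline is the same whether one subject or six had a rise of that size. It gives the size of the extreme and no count, and it is not tied to a reference range. The listings hold every value but tabulate nothing.

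**The case against.** The strongest reply is that baseline-referenced information is already planned. Opposite changes cancel in a mean, but the minimum and maximum change do not cancel, and opposite changes widen the SD. The largest within-subject rise in ALT or creatinine would appear at each time point, by cohort and overall. Listings cover every scheduled and unscheduled value, and about 30 subjects can be read one by one. Protocol 8.1.5 is a rule for recording adverse events and does not prescribe a table. Investigators judge out-of-range values for clinical significance (Protocol 7.2.3.5), and SAP 4.9.1 tabulates treatment-emergent events, including those that began before dosing and worsened. SAP 5.1 does not list Protocol 9.8 among its changes, so the commitment on potentially clinically important findings was not withdrawn.

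All of this stands, and it limits the point. A reader might infer that new abnormalities are in fact hidden, that many subjects enter abnormal, or that hepatic or renal injury would go unseen. The documents support none of these. They give no baseline abnormality rate, exclusion 9 is a ceiling given by way of example, and the complications listed are those of convulsive status epilepticus only.

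What remains is narrower. None of these outputs gives the number of subjects with new or worsened abnormalities. The adverse event route depends on investigator judgment, and the Protocol 9.8 commitment has no criteria in the SAP to make it work.

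**Conclusion.** The point holds as a weakness of one table. The planned count mixes baseline, new and resolved abnormalities and is blind to worsening, in a single-arm study where the subject's own baseline is the only comparison. Its possible size runs from nothing to min(b, 30 − b) offset cases per parameter. Where in that range it falls depends on baseline abnormality and resolution rates that the documents do not give. The illustrations assume N = 30 and no missing values.

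No test or estimate is biased, because the SAP is descriptive throughout, and no subject-level data are lost. The change should be made because it is better matched to the question and cheap, but no conclusion of the study fails without it.

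**What to change.** In SAP 4.9.6, replace or supplement the abnormal-results table as follows.

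1. Add a shift table of baseline category (low, normal, high) against worst post-baseline category for each parameter, overall and by cohort, with unscheduled values included.
2. Add the number newly abnormal, by direction, over subjects normal at baseline who have at least one post-baseline value. State that this denominator overrides the SAP 4.4 default.
3. Show subjects without a pre-dose value on a separate line. Both schedules allow the first sample within 2 hours of drug initiation, and such a value cannot serve as baseline under SAP 4.4.
4. For subjects abnormal at baseline, report crossings of limits already in the protocol: ALT or AST above 5 times ULN, bilirubin above 2 times ULN, and eGFR at or below 45 mL/min. These are descriptive reporting cut-points only. The eGFR limit is written as below 45 in the synopsis and as at or below 45 in Protocol 4.2 and 4.5.1; the wording should be reconciled first.

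The cost is SAP text and one reprogrammed table, using results and local laboratory reference ranges already collected. There are two limitations. With about 30 subjects in three cohorts the cells will be sparse, so the overall column carries most of the information. The limits in item 4 do not cover electrolytes or glucose, so for those parameters only a change of category would be seen.
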